4.3.1 Criteria

No subject randomized into this trial who discontinues treatment for any reason will be replaced.

Unless required for safety reasons (i.e., medical treatment of SAEs), subjects eligible for an exit DBPCFC will not be unblinded earlier than their scheduled DBPCFC. Subjects who are considered escalation failures will be unblinded no sooner than Week 24.

Any subject may be prematurely terminated from additional allergen exposures for the following reasons:

- Life-threatening symptoms (CoFAR Grade 4; refer to Table A4-3 in Appendix 4), including, but not limited to, anaphylaxis resulting in hypotension, neurological compromise, or mechanical ventilation secondary to peanut OIT dosing or any peanut food challenge
- 2. Severe symptoms (CoFAR Grade 3; refer to **Table A4-3** in **Appendix 4**), including, but not limited to, those that require aggressive therapy (to be determined by the investigator, but may include such interventions as IV epinephrine, intubation, or admission to an intensive care unit) or those that are recurrent
- 3. Poor control or persistent activation of secondary atopic disease (e.g., atopic dermatitis, asthma)
- 4. Started on ARBs, ACE, beta-blockers, or other prohibited medications, with no alternative medications available per the prescribing doctor

- 5. Pregnancy
- 6. Circumstances (e.g., concurrent illness, such as gastroenteritis) requiring missed peanut OIT maintenance dosing of > 7 consecutive days
- Non-adherence with home peanut OIT dosing protocol (excessive missed days; i.e., > 3 consecutive days missed on 3 or more occasions) would be a safety issue warranting discontinuation

Any subject may also be prematurely terminated from the study if:

- 8. The subject elects to withdraw consent from all future study activities, including follow-up.
- 9. The subject is "lost to follow-up" (i.e., no further follow-up is possible because attempts to reestablish contact with the subject have failed).
- 10. The subject develops biopsy-documented eosinophilic esophagitis (EoE).
- 11. The subject's continued participation in the study is assessed by the investigator to constitute a threat to the safety of the subject or the safe conduct of the study
- 12. The subject dies (CoFAR Grade 5)

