dose reduction) or a 2-step dose reduction as their next day's dose (Day 3) in the Clinical Research Center. If this dose is tolerated, it will be continued as the daily home dose for the normal time interval, then escalation attempted in the Clinical Research Center as noted below. If this dose is not tolerated, then the next dose will be a further 1-2-step reduction in dosing (per investigator judgment), and the dose will be given in the Clinical Research Center (Day 4). If this next dose is not tolerated, then a discussion with the Medical Monitor will ensue to make a decision about whether to continue the subject on study-product treatment in the study.

If more *severe symptoms* occur, defined as:

- Skin severe generalized urticarial/angioedema/erythema
- Respiratory laryngeal edema, throat tightness with hoarseness, wheezing with dyspnea, stridor
- GI significant severe abdominal pain/cramping/repetitive vomiting and/or diarrhea
- Neurological change in mental status
- Circulatory clinically significant hypotension (see Appendix 3).

The action should be to treat the subject, and at the physician's discretion either 1) have them return to the Clinical Research Center the next day (Day 2) for dosing with a 2-step reduction in dose under observation or 2) discontinue them from the study product treatment. If the subject tolerates the dose reduction, then they will remain on that dose for 2 weeks and then return to the Clinical Research Center for the dose escalation. A discussion with the Medical Monitor may ensue to make a decision about whether to continue the subject on study product treatment in the study.

If a subject fails dose escalation after three consecutive attempts (with 2-4 weeks between), he/she will be considered an escalation failure and the last tolerated dose will be accepted as the maintenance dose (to Week 24). If the dose escalation is completed with no symptoms, subjects should be observed for 30 min. If the subject exhibits mild symptoms, the duration of the observation period should be 1-2 h post-protocol. For moderate to severe symptoms, the observation period should be at least 4 h and up to 24 h based on symptoms and the treatment regimen needed to stabilize the subject's condition.

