Any subject deemed to have severe symptoms including hypoxia, hypotension, or change in mental status (stage 3 anaphylaxis defined in **Appendix 3**) or who receives aggressive therapy (to be determined by the investigator, but may include such interventions as IV epinephrine, intubation, or admission to an intensive care unit) for an allergic reaction at any time should be discussed with the Medical Monitor and discontinued from study product therapy.

For specific questions related to dosing escalation or continuation of the same dose that are not answered in the above protocol, the Medical Monitor will be available for questions.

Any subject who discontinues build-up dosing due to repeated allergic reactions to the characterized peanut allergen will have his/her mechanistic blood draw (refer to **Section 8**) within approximately 1 week of discontinuation of therapy.

6.8.3 Treatment for Reactions During the Build-up Phase: Pharmacological and Supportive Treatments

Treatment of individual reactions should be with either an antihistamine and/or epinephrine, along with IV fluids, a beta-agonist (e.g., albuterol, by inhaler or nebulizer), oxygen, and glucocorticosteroids, as indicated. Generally, for mild symptoms requiring treatment, the subject should receive antihistamines. Generally, for moderate symptoms requiring treatment, the subjects should receive antihistamines and/or epinephrine, as indicated. If severe anaphylaxis (stage 3 anaphylaxis defined in **Appendix 3**) occurs at any time, dose escalation will stop and the dose will be reduced to the last tolerated dose and the subject continued on that dose as long-term maintenance without further escalation.

Antihistamines

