If a single administration of epinephrine is required during escalation in the clinic, the dose of study medication is to be reduced by two increments, or to the last tolerated dose (at the physician's discretion), and dose escalation is to continue.

If a single administration of epinephrine is required a second consecutive time during this escalation attempt, the dose should be reduced by two doses, and the subject continued on that dose for 6-8 weeks. After 6-8 weeks at the reduced dose, an escalation attempt may be tried in clinic.

If a single administration of epinephrine is required a third consecutive time during this escalation attempt, the dose should be reduced by two doses and the subject continued on that dose as long-term maintenance (to Week 24) without further escalation. (Note: an event requiring 3 consecutive administrations of epinephrine is to be reported within 24 hours of its occurrence, see Section 7.1 and 7.7.2). The subject will continue to be followed for safety biweekly (following their established visit schedule) while continuing to be dosed at their last tolerated dose level until Week 24. Dosing will be stopped after the Week 24 Visit; and the subject will be asked to return to the Clinical Research Center 14 days following their last dose of study product to undergo an Early Discontinuation Visit (see Section 6.5). For subjects who halt dose-escalation after Week 24, there will be no maintenance phase. Dosing in these subjects will be discontinued when dose-escalation is stopped. They will be asked to return to the Clinical Research Center 14 days following their last dose of study product to undergo an Early Discontinuation Visit (see Section 6.5). No additional DBPCFC will be performed.

Epinephrine - Home

If a single administration of epinephrine use occurs during dosing at home, this epinephrine use is not counted as one of the uses described above, unless severe anaphylaxis is assessed to have occurred at home. The subject should return to clinic for an observed dose prior to resuming any dosing at home.

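### Between the end of Visit 01 and Week 24, Protocol 6.8.2 stops study product after stage 3 anaphylaxis while 6.8.3 continues it, and nothing readable says which rule governs

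*Protocol*

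**What the plan says.** **Protocol 6.8.2, near its end.** The rule covers "Any subject deemed to have severe symptoms including hypoxia, hypotension, or change in mental status", identifies these as stage 3 anaphylaxis under Appendix 3, and adds anyone given aggressive therapy. A subject with such a reaction "at any time should be discussed with the Medical Monitor and discontinued from study product therapy".

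**Protocol 6.8.3, opening paragraph.** If stage 3 anaphylaxis under Appendix 3 occurs at any time, escalation stops, "the dose will be reduced to the last tolerated dose and the subject continued on that dose as long-term maintenance without further escalation".

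Four other places touch the same event:

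- **Protocol 6.8.2, severe-symptom paragraph.** Its list includes change in mental status and "Circulatory clinically significant hypotension (see Appendix 3". At the physician's discretion the subject is either discontinued or re-dosed two steps lower. In the second case, "If the subject tolerates the dose reduction, then they will remain on that dose for 2 weeks and then return" for escalation.
- **Protocol 6.8.3, Epinephrine - Home.** After a single home administration, "this epinephrine use is not counted as one of the uses described above, unless severe anaphylaxis is assessed to have occurred at home". Under Epinephrine - Clinic, a first use leads to a lower dose, "and dose escalation is to continue".
- **Protocol 4.3.1**, to which 7.9.2 refers for further individual stopping rules: "Any subject may be prematurely terminated from additional allergen exposures for the following reasons". The verb is permissive.
- **SAP 3.2.2** cites protocol 6.8.2 and 6.8.3 together for dosing to Week 24 after halted escalation, with no exception for stage 3.

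**The concern.** Study product is either stopped or given daily. A site that reads 6.8.2 stops it, and a site that reads 6.8.3 sends the subject home on it. No action satisfies both. The subject is a child or young adult who has just had hypoxia, hypotension or neurological compromise, and SAP 3.2.2 places dosing between clinic visits at home. Follow-up differs too: an Early Discontinuation Visit 14 days after the last dose under one rule, biweekly visits to Week 24 under the other. About 8 sites are expected (Protocol 6.1), so the same event could be handled differently from site to site.

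**Working it through.** The plan gives no figure on this point, so the main check is a comparison of the texts.

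**1. The two rules side by side**

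| | 6.8.2 | 6.8.3 |
|---|---|---|
| Trigger | Stage 3 anaphylaxis, or aggressive therapy | Stage 3 anaphylaxis |
| Definition | Appendix 3 | Appendix 3 |
| Timing | Any time | Any time |
| Medical Monitor | Discussion required | Not mentioned |
| Study product | Discontinued | Continued at last tolerated dose |

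For stage 3 events, trigger, definition and timing coincide and the actions are opposite.

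**2. When the conflict is live**

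- *Visit 01.* Section 6.8.1 governs and discontinues after severe symptoms at any dose. (The Table 3-1 note on Day 2 reactions to 6 mg is looser, but that is separate from the two build-up rules compared here.)
- *End of Visit 01 to Week 24.* 6.8.2 stops dosing. 6.8.3 continues it, and 6.8.4 carries halted subjects on their last tolerated dose to Week 24. Section 6.8.4 also applies the build-up rules to reactions during maintenance. The conflict is direct.
- *After Week 24.* Section 6.8.4 gives no maintenance phase to subjects whose escalation halts, so dosing stops under either rule.

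**3. What the choice means in doses**

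Inputs: the dose ladder in Tables 3-1 and 3-2 (3, 6, 12, 20, 40, 80, 120, 160, 200, 240, 300 mg), one step every 2 weeks, and 300 mg reached at about Week 18 or 20 (SAP 3.2.2). Assumptions: the reaction occurs at an on-schedule clinic up-dosing visit, and the last tolerated dose is one step below.

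Further daily doses under 6.8.3 = (24 - week of event) x 7. Under 6.8.2 the number is 0.

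| Start | Event | Further doses under 6.8.3 |
|---|---|---|
| 6 mg | 12 mg, Week 2 | 22 x 7 = 154, at 6 mg |
| 6 mg | 120 mg, Week 10 | 14 x 7 = 98, at 80 mg |
| 6 mg | 300 mg, Week 18 | 6 x 7 = 42, at 240 mg |
| 3 mg | 300 mg, Week 20 | 4 x 7 = 28, at 240 mg |

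These are illustrations, not limits. Delayed up-dosing can bring the event close to Week 24 and the difference close to 0. A home reaction before Week 2 could give more than 154.

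**4. How often**

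Protocol 1.6.1 expects severe symptoms in under 1% of subjects. About 50 subjects randomized 1:1 gives about 25 on active treatment. Expected number: below 25 x 0.01 = 0.25. Chance of at least one: below 1 - 0.99^25 = 0.222, or about 22%. Stage 3 is only part of what 6.8.2 calls severe, so the stage 3 figures would be lower.

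**5. Effect on the primary endpoint**

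During up-dosing, escalation ends under both rules. The subject does not reach 300 mg/day, has no exit DBPCFC, and is an escalation failure and non-responder under SAP 7.3 and Table 7.1, outside the ad libitum exception. The choice between the rules does not change the classification.

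**The case against.** The best case for leaving the text alone is that a competent site would discontinue. Section 6.8.2 brings in the Medical Monitor. Section 7.9.2 treats 4.3.1 as holding stopping rules, which is compatible with discontinuation and makes 6.8.3 look like the outlier. Whichever sentence a site follows, severe anaphylaxis must be reported to the Coordinating Center within 24 hours and relayed to the sponsor and DMC (7.1, 7.7.2). The event should be rare. Figure 6-2, not visible in the text reviewed, may show the intended action.

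Much of that stands: the rarity, the prompt reporting, and the hint about which rule was meant. It does not settle the dosing instruction. In 6.8.2 the Medical Monitor discussion is joined to discontinuation, not offered as an alternative to it. The contrast between should in 6.8.2 and will in 6.8.3 does not reconcile them. Both rules are equally specific, so neither yields as the general one. Reporting does not tell the site what to give the next day. A figure could support one sentence but would not delete the other.

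Three stronger readings are tempting and are not supported.

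- A reader might infer that the conflict runs through the whole study. Sections 6.8.1 and 6.8.4 confine it to the window above.
- A reader might infer further rules that allow re-escalation after stage 3, from the severe-symptom paragraph and Epinephrine - Home. The severe-symptom paragraph can be read as yielding to the specific stage 3 rule, and the home clause can be read the same way. The uses to which that clause refers may also be those under Epinephrine - General, which covers clinic and home and halts escalation after two or more doses for a reaction. These are ambiguities to tidy, not demonstrated conflicts.
- A reader might infer bias or lost power. During up-dosing the subject is a non-responder under either of the two rules.

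**Conclusion.** The conflict is real and should be fixed. For stage 3 anaphylaxis from the end of Visit 01 to Week 24, 6.8.2 and 6.8.3 cannot both be followed, and no readable text gives one precedence. The consequence for the subject is 0 further doses against, for example, 154 after a Week 2 event or 42 after a Week 18 event, assuming on-schedule up-dosing and maintenance to Week 24. On the protocol's own expectation fewer than 0.25 active subjects would have any severe reaction, so the case for the change is the gravity of the event and not its frequency. It is a drafting inconsistency in a safety rule that affects subject safety and uniform conduct across sites. Figure 6-2 could not be checked.

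**What to change.** Replace the stage 3 sentence in 6.8.3 with: *If severe anaphylaxis (stage 3, Appendix 3) occurs at any time, study product is discontinued, the Medical Monitor is informed, and the subject returns for an Early Discontinuation Visit 14 days after the last dose (Section 6.5).*

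For consistency:

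- Limit the re-dosing option in the 6.8.2 severe-symptom paragraph to reactions below stage 3.
- State in Epinephrine - Home that severe anaphylaxis at home follows the stage 3 rule.
- Check Figure 6-2 against the rule chosen.

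Do not make 4.3.1 item 1 mandatory. That item is defined by CoFAR Grade 4, whereas Section 7.5 makes anaphylaxis staging independent of toxicity grade, and Table A4-3 puts transient hypotension at Grade 3. The item also covers food challenges, so a mandatory rule could bar a subject who passes 300 mg at the exit DBPCFC and reacts at 600 mg from further exposure, and so affect rollover to ARC002.

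If the sponsor does intend maintenance dosing after stage 3, 6.8.2 should be changed to match and the choice justified.

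Cost: three wording edits, a check of one figure and a note to sites, with no new data or subjects. The downside is that a subject who might have tolerated a lower maintenance dose stops treatment.

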6.8.4 Reactions During Maintenance Phase

This phase consists of the subject receiving the maximum achieved daily dose of peanut OIT.

Subjects who fail escalation during the initial escalation period (Visit 1; Days 1 to 3), i.e., subjects who do not tolerate a minimum of 3 mg of study product (CPNA or matching placebo), will stop dosing and will not enter a maintenance phase. These subjects will be followed for safety and be asked to return to the Clinical Research Center 14 days following their last dose of study product to undergo an Early Discontinuation Visit (see, **Section 6.5**).

Subjects whose up-dosing is halted because of failing subsequent build-up (i.e., after the initial escalation period; Visit 1), will continue to be dosed at the last tolerated dose level and to be followed for safety biweekly (following their established visit schedule) until Week 24. The length of time from the cessation of up-dosing to Week 24 will constitute the maintenance phase for these subjects. The maintenance phase, thus, may vary in length from subject to subject. Dosing will be stopped after the Week 24 Visit; and the subject will be asked to return to the Clinical Research Center 14 days following their last dose of study product to undergo an Early Discontinuation Visit (see, Section 6.5).

There will be no maintenance phase for subjects who halt dose-escalation after Week 24. Dosing in these subjects will be discontinued when dose-escalation is stopped. They will be followed for safety and asked to return to the Clinical Research Center 14 days following their last dose of study product to undergo an Early Discontinuation Visit (see Section 6.5).

Subjects who achieve the targeted dose of 300 mg/d by Week 34 will then enter a 2-week maintenance phase. For these subjects, the maintenance phase will be followed by a DBPCFC performed at their Exit Visit (no later than week 36; see, Section 6.5).

All subjects will continue to follow a peanut-restricted diet for the duration of the study.

For any noted symptoms during the maintenance phase, the **same** study dosing rules for the build-up phase will be followed.

Figure 6–2. Schematic for Build Up Phase Dose Escalation – Day of Symptom

6.9 Missed Peanut OIT Doses at any Phase of the Study:

Missed Peanut OIT doses at any phase of the study can pose a significant risk to the enrolled subjects. The algorithm for missed consecutive doses of study product is as follows:

- Miss 1 dose The next dose would be the current dose and could be given at home
- Miss 2 doses in a row The next dose would be the current dose and could be given at home
- Miss 3 doses in a row The next dose would be the current dose and would be given under observation (Clinical Research Center)
- Miss 4 doses in a row The next dose would be the current dose and would be given under observation (Clinical Research Center)
- Miss 5-7 doses in a row –Initiate the next dose as approximately 25% of the last tolerated dose. This would be done under observation (Clinical Research Center). Dose escalation would occur in the Clinical Research Center with an escalation no sooner than weekly and no longer than every 4 weeks with dose increases of 1-dose levels at each escalation. If symptoms occur, the dosing symptom rules in the build-up phase would apply
- Missing >7 consecutive days of therapy constitutes an individual stopping rule and the subject would no longer take the study product. The subject will be asked to return to the Clinical Research Center 14 days following their last dose of study product to undergo an Early Discontinuation Visit (see Section 6.5)
- Additionally; excessive missed doses, i.e., > 3 consecutive days missed on 3 occasions, constitutes an individual stopping rule and the subject would no longer take the study product. The subject will be asked to return to the Clinical Research Center 14 days following their last dose of study product to undergo an Early Discontinuation Visit (see Section 6.5).

No attempt should be made to make up for a missed dose if greater than 6 hours have elapsed since usual time of dosing.

6.10 Double-Blind Placebo Controlled Food Challenge

The subject will be off antihistamines for an appropriate length of time (5 half-lives of the antihistamine that is being used). Oral food challenges will be undertaken under direct medical supervision in a Clinical Research Center or food challenge area with emergency medications and staff immediately available and will follow established study procedures. Prior to the DBPCFC, subjects will be assessed for an exacerbation of asthma as determined by active wheezing or a peak expiratory flow rate < 80% of predicted. A uniform approach for food challenges will be used. Frequent assessments will be made for symptoms affecting the skin, gastrointestinal tract, cardiovascular system, and/or respiratory tract. Dose limiting symptoms, typically objective symptoms (signs), indicate a positive reaction and termination of dosing.

6.11 Skin Prick Test

Subjects will have skin prick tests performed using study approved procedures for food allergens. While the subject is off antihistamines for an appropriate length of time (5 half-lives of the antihistamine that is being used), a skin test probe is pressed through a commercial extract of an allergen into the epidermis. Positive (histamine) and negative (saline-glycerin) controls are placed to establish that the response is not blocked and to determine if there is dermatographism, respectively.

6.12 Visit Windows

Dosing schedule should be adhered to strictly. Two days before, or 2 days after a planned dosing visit, is an acceptable window with continued daily dosing of the current dose level. Study visits for scheduled blood draws or DBPCFC should take place within 2 weeks of the scheduled visit.

6.13 Study Blinding Procedures

The study is double-blinded up to completion of the exit DBPCFC, escalation failure, or endpoint failure.

Those who are not eligible for the DBPCFC at Week 34 will be unblinded at this time.

Those who do not pass the DBPCFC at Week 36 will be unblinded at this time.

All food challenges are performed in a double-blind manner.

